Appendix D – Effect of mPATH on Screening for Depression, Fall Risk, and Safety

Wake Forest policy requires primary care clinics to screen patients aged 18 and older for depression, fall risk, and safety at home at each provider visit. Nursing staff conduct this screening during the rooming process by asking patients standardized questions and recording their responses in the electronic health record.

We designed mPATH to save staff time by having patients answer these same screening items on an iPad and then transmitting their answers to WakeOne. It is possible that mPATH will increase detection of depression, fall risk, and safety concerns because: 1) mPATH systematically asks these screening items of all patients, and 2) patients may feel more comfortable answering these items in an iPad survey than during an in-person interview.

To determine the effect of mPATH on the performance of this screening, we will examine a limited use dataset comparing the 2 months before a clinic started using mPATH to the 2 months after the clinic began using mPATH. Because clinics may need some time to fully adopt mPATH, we will exclude the first two weeks following the launch of mPATH.

Study Population

We will create a limited use dataset containing patients who are seen in one of the first six Wake Forest Baptist Health primary care clinics that are participating in the mPATH Effectiveness and Implementation trial.

Patient inclusion criteria:

- Age 18 or older
- Completed a provider visit at the study clinic during the 60 days prior to the clinic launching the mPATH program (the “pre” time period), or completed a provider visit at the study clinic during days 14 – 73 after the launch of mPATH (the “post” time period)
- Have a preferred language of English or Spanish

Patient exclusion criteria:

- Requiring a language interpreter for a language other than Spanish

Experimental Methods

The limited use dataset will contain the following data elements for each completed patient visit:

Protocol version date
7/29/2021

EFFECTIVENESS AND IMPLEMENTATION OF MPATH-CRC: A MOBILE HEALTH SYSTEM
FOR COLORECTAL CANCER SCREENING
Wake Forest Baptist Comprehensive Cancer Center (WFBCCC)
WFBCCC # TBD

- Date of clinic visit (where each date is indicated by a number relative to the clinic's Launch Date)
- Clinic (designated by a unique study clinic identifier)
- Type of visit completed (for example, new patient visit, return patient visit, annual exam)
- Patient age
- Patient gender
- Patient race/ethnicity
- Patient primary insurance
- Nursing staff who roomed the patient (designated by a unique study identifier)
- Whether patient used mPATH-CheckIn program (Y/N)
- Whether nursing staff used mPATH Nursing Module to transmit mPATH data to WakeOne (Y/N)
- Whether patient has a diagnosis of depression in the problem list in the EHR (Y/N)
- Whether patient has an antidepressant medication listed in the active medication list (Y/N)
- Results of depression screening items
- Results of fall risk screening items
- Results of safety at home screening items

The study dataset will be maintained using the procedures outlined in **Section 8.0 (Confidentiality and Privacy)**. Of note, we are taking the following additional safeguards to further protect patient confidentiality:

1. Dates of clinic visits will be designated using numbers relative to each clinic's launch date, rather than using the actual date
2. Clinics will be designated with a unique study clinic identifier instead of clinic name
3. Nursing staff will be designated with a unique study identifier instead of actual name

Definition of Time Periods

- The day a clinic launches mPATH will be designated as that clinic's Day 0
- The "pre" time period will be Days -60 to -1 (the 60 day period before mPATH Launch)
- The "post" time period will be days 14 to 73 (the 60 day period commencing 2 weeks after mPATH Launch)

Outcome Measures

Protocol version date
7/29/2021

EFFECTIVENESS AND IMPLEMENTATION OF MPATH-CRC: A MOBILE HEALTH SYSTEM
FOR COLORECTAL CANCER SCREENING
Wake Forest Baptist Comprehensive Cancer Center (WFBCCC)
WFBCCC # TBD

Primary outcome: The primary outcome will be the proportion of patients seen in each time period (“pre” vs. “post”) who screen positive for depression, fall risk, or safety concerns at home.

Secondary outcomes: Secondary outcomes will include the proportion of patients in each time period who:

- Screen positive for depression using the PHQ-2 items. In addition, the outcomes below will be assessed:
 - Have a PHQ9 score >14 (indicating moderately severe depression or severe depression)
 - Have a PHQ9 score >19 (indicating severe depression)
 - Have a PHQ9 score >14 and are not currently taking a medication for depression
 - Have thoughts of self-harm
- Screen positive for fall risk at home. In addition, the outcomes below will be assessed:
 - Have fallen in last 6 months
 - Have had a fall with injury
- Screen positive for safety concerns at home. In addition, the outcome below will be assessed:
 - Report that conflicts turn into fights

Analytic plan

Our primary analysis will compare the proportion of patients seen in the “pre” time period to the “post” time period who screen positive for either depression, fall risk, or safety at home. If a patient is seen more than once in a given time period, only the patient’s first visit in that time period will be included in the analyses. We will estimate the proportion who screen positive for each time period and report along with 95% confidence intervals. A chi-square test will be used to provide an unadjusted comparison between the “pre” and “post” proportions. Logistic regression models will then be used to compare the “pre” and “post” proportions while controlling for clinic and patient demographic variables. We will use the same analytic methods for our secondary outcomes. We will also conduct a sensitivity analysis for our primary outcome where we consider all patients’ visits during a given time period (and not limit analyses to a patient’s first visit in the time period only). For this sensitivity analysis, we will compare the proportion of patients who meet our primary outcome definition at any visit during the “pre” and “post” time periods.

Analytic adjustments due to COVID19 pandemic: Due to the COVID19 pandemic, all practices stopped using mPATH in March 2020, which is prior to the closure of the 60-day “post” time period for clinics #5 and #6 in our sample. Therefore, we will truncate Protocol version date

7/29/2021

EFFECTIVENESS AND IMPLEMENTATION OF MPATH-CRC: A MOBILE HEALTH SYSTEM
FOR COLORECTAL CANCER SCREENING
Wake Forest Baptist Comprehensive Cancer Center (WFBCCC)
WFBCCC # TBD

the “post” time period for these two clinics to 30 days. To determine if this truncated time period affected our overall results, we will conduct the following sensitivity analyses: (1) limiting the analyses to only the first 4 clinics to enroll, and (2) limiting data collection to 30-days post- for all 6 clinics.

Protocol version date
7/29/2021

EFFECTIVENESS AND IMPLEMENTATION OF MPATH-CRC: A MOBILE HEALTH SYSTEM
FOR COLORECTAL CANCER SCREENING
Wake Forest Baptist Comprehensive Cancer Center (WFBCCC)
WFBCCC # TBD

Protocol version date
7/29/2021

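### Patients seen in both periods count in both samples of a pre-post comparison that assumes independent records; shared nurses may also distort precision, and the net effect is unknown

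*Combined protocol and SAP*

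**What the plan says.** All references are to Appendix D.

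- **Who enters.** Study Population admits a patient with a visit in either window. Nothing excludes or links a patient who has a visit in both. Under Analytic plan, only the patient's "first visit in that time period will be included in the analyses", so repeats are removed within a window and not across windows.
- **Estimates and tests.** For the primary outcome: "We will estimate the proportion who screen positive for each time period and report along with 95% confidence intervals". The comparison comes next: "A chi-square test will be used to provide an unadjusted comparison between the" two proportions. Logistic models then compare the "proportions while controlling for clinic and patient demographic variables". The rare outcomes get the same treatment: "We will use the same analytic methods for our secondary outcomes".
- **Nurses.** The opening text says that nursing staff put the items to patients and record the answers in usual care. Experimental Methods lists, for each visit, "Nursing staff who roomed the patient (designated by a unique study identifier". The Analytic plan does not use this variable.
- **What is not named.** There is no nurse term, clustered variance, GEE, mixed model or paired test. The planned sensitivity analyses (all visits, first four clinics, 30 days post for all clinics) address neither source of dependence.
- **Target.** Outcome Measures says "The primary outcome will be the proportion of patients seen in each time period", which can be read as describing these patients only. The opening text aims to learn what mPATH does to how screening is carried out, which is broader. The plan does not choose between them.

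**The concern.** Two kinds of dependence are built into the data.

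The first is the patient. These are primary care clinics, the windows are only two weeks apart, and return visits are among the listed visit types, so some patients will probably appear in both samples. The same person answering the same items twice is likely to give correlated answers. A two-sample test that ignores this overstates the variance of the difference and loses power.

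The second is the nurse. If nurses differ in how they ask or record, patients roomed by the same nurse resemble one another. That can make each period's interval too narrow. It can also make the pre-post standard error too small, if the nurse contribution does not cancel between periods. The plan itself gives a reason why it might not: the iPad asks every patient in the same systematic way and may feel easier than an interview.

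At stake are the stated precision of each proportion and the p-value for the primary comparison.

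**Working it through.** **Inputs.** From Appendix D: six clinics, pre window days −60 to −1, post window days 14 to 73, one record per patient per window, 95% intervals. The documents give no sample size, positive rate, alpha, nurse count, caseload, intra-nurse correlation (ICC) or patient overlap. There is therefore no figure of the plan's to reproduce. Every other input below is assumed, with alpha nominally 5%.

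**Step 1: patients in both periods.** Let n1 and n2 be the sample sizes, k the number of patients in both, p the common positive rate and c the within-patient correlation (for the logistic model, what remains after clinic and demographics).

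- Planned variance of the difference: p(1−p)(1/n1 + 1/n2).
- True variance: the same, minus 2kc·p(1−p)/(n1·n2).
- Ratio of true to planned: 1 − 2kc/(n1+n2) = 1 − fc, where f is k divided by the mean sample size.
- True alpha: 2[1 − Φ(1.96/√ratio)].

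| f | c | ratio | planned SE / true SE | true alpha |
|---|---|---|---|---|
| 0.20 | 0.5 | 0.90 | 1/√0.90 = 1.05 | 3.9% |
| 0.40 | 0.5 | 0.80 | 1/√0.80 = 1.12 | 2.8% |

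This step needs no assumption about nurses or the inference target. A simulation at f = 0.40 and c = 0.5 gave alpha of 2.8% as planned and about 5.5% with patient-clustered errors.

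**Step 2: per-period intervals, if nurses are regarded as a sample.** With m patients per nurse, D = 1 + (m−1)·ICC and coverage = 2Φ(1.96/√D) − 1.

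| ICC | D, m = 50 | coverage | D, m = 150 | coverage |
|---|---|---|---|---|
| 0.002 | 1.098 | 94% | 1.298 | 91% |
| 0.005 | 1.245 | 92% | 1.745 | 86% |
| 0.01 | 1.49 | 89% | 2.49 | 79% |

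In points: with 20% positive and 3,000 patients, the half-width is 1.96·√(0.2·0.8/3000) = 1.4. At m = 100 and ICC 0.01, D = 1.99 and the half-width becomes 1.4·√1.99 = 2.0.

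If the six clinics are fixed strata with different rates, the pooled binomial variance already contains some clinic spread. The ICC must then exceed a small threshold before the interval is too narrow. For assumed clinic rates of 0.10 to 0.30 this is about 0.0014 at m = 20 and 0.0003 at m = 100.

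**Step 3: pre-post comparison with both sources.** Let r be the correlation of a nurse's effect between periods. D = 1 + (m−1)·ICC − m·ICC·r − fc. At m = 100 and ICC 0.01 this is 1.99 − r − fc.

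| r | D, no overlap | alpha | D, f = 0.20, c = 0.5 | alpha |
|---|---|---|---|---|
| 1 | 0.99 | 4.9% | 0.89 | 3.8% |
| 0.95 | 1.04 | 5.5% | 0.94 | 4.3% |
| 0.8 | 1.19 | 7.2% | 1.09 | 6.0% |
| 0.5 | 1.49 | 10.8% | 1.39 | 9.6% |

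- At ICC 0.002 with the same overlap, D = 1.098 − 0.2r, so alpha runs from 3.9% (r = 1) to 5.0% (r = 0.5).
- If nurse effects are stable but loads within a clinic move from 100 each to 40/70/100/130/160, D = 1 − 0.01 + 0.01·9000/(2·500) = 1.08 and alpha is 5.9%.
- The rows with r below 1 assume equal ICC in both periods and nurse-specific changes that average zero.

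**Step 4: behaviour of the remedies.** Simulated with 2,000 replicates per case (error about 0.5 points), 6 clinics of 5 nurses, 100 patients per nurse per period, 20% positive, c = 0.5. Two-way means clustering by nurse and by patient.

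| Case | alpha as planned | alpha two-way |
|---|---|---|
| ICC 0, f = 0.4 | 3.2% | 6.2% |
| ICC 0.01, r = 1, f = 0.4 | 3.2% | 5.9% |
| ICC 0.01, r = 0.8, f = 0.2 | 6.0% | 5.0% |
| ICC 0.01, r = 0.5, f = 0.2 | 9.2% | 4.5% |
| ICC 0.01, nurse variation pre only, f = 0.2 | 10.2% | 5.3% |

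Pre-period coverage at ICC 0.01 was 81% to 85% as planned and 93% to 96% with nurse clustering within clinic. For an outcome with 0.3% positive (about 9 events per period), some clinic had no events in 33% of replicates.

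**The case against.** **The inference target is not stated.** Conditional on the observed nurses, the per-period intervals are not too narrow. Treating nurses as a sample while holding the six clinics fixed is a reviewer's choice. This stands, so the nurse point must be conditional. The intervals also only accompany the primary analysis, which is the pre-post comparison.

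**A reader might infer that the pre-post standard error is simply wrong.** The documents do not support that. With stable nurses and no overlap alpha is 4.9%, and at ICC 0.002, 20% overlap and r = 0.5 it is 5.0%. The errors can cancel.

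**A reader might take the COVID-19 adjustment as evidence of shifting loads**, because it cuts the post "time period for these two clinics to 30 days". It is not. Truncation changes a whole clinic's volume, and clinic is already in the model. If nurses' shares within the clinic are unchanged, stable nurse effects still cancel. A check at ICC 0.01, r = 1 and no overlap gave alpha of 5.1% with post loads halved in two clinics and 5.3% without (6,000 runs).

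**Nurse variation may be small, especially post.** The questions are standardized. If patients answer on an iPad, the post-period ICC may fall, so the post interval may need little widening. Both points are fair, and the documents measure neither.

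**The overlap error is conservative, and two-way errors can overshoot.** This stands too: alpha reached 6.3% in the least favourable case, where loads were reshuffled in both periods and clinics #5 and #6 were halved post. It is a reason to make patient clustering the core change and nurse clustering a secondary layer. It is not a reason to keep a test that ignores known pairing.

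**Conclusion.** The concern holds in two parts of unequal strength.

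1. **Patient overlap.** This follows from the text. With any overlap and positive within-patient correlation, this source alone makes the planned pre-post standard error too large. The 5% and 12% figures rest on assumed overlap of 20% and 40% and an assumed correlation of 0.5. Only the size is open.
2. **Nurses.** This is conditional. The per-period intervals may be too narrow if inference extends beyond the observed nurses. The pre-post standard error may be too small if nurse effects, staff or within-clinic loads change. The coverage and alpha figures are illustrations and not estimates for this study.

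The net direction for the primary comparison cannot be read from the documents, and the net error may be near zero. The change is still worth making, because the inputs are unknown and the data can supply the variance directly.

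**What to change.** - **Core change.** Keep a coded patient link across the two periods. Base the clinic-adjusted pre-post comparison on patient-clustered standard errors (GEE or robust). Label the plain chi-square as descriptive.
- **Sensitivity analysis.** Using the nurse identifier already collected, repeat the comparison with errors clustered also by nurse, with a small-sample correction (t with number of nurses minus 1 degrees of freedom). Report nurse-clustered per-period intervals within clinic.
- **Target.** State whether inference is conditional on the observed nurses and on the six clinics. Note that nurse clustering does not capture clinic-by-period variation.
- **Sparse secondary outcomes.** Report them descriptively, for example when a clinic has no events.

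**Cost.** Analysis-plan wording and slightly more modelling. The listed data elements do not name a patient link, although the first-visit rule already needs one within each period. Some intervals may widen, and the two-way errors are only approximate.

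### Patients seen in both periods enter the pre/post comparison twice, but the planned tests treat all rows as independent, and no patient identifier is listed

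*Combined protocol and SAP*

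**What the plan says.** All references are to Appendix D of the combined protocol and SAP.

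- **Study Population.** A patient qualifies through a visit in the 60 days before launch, "or completed a provider visit at the study clinic during days 14" to 73 after it. The only exclusion concerns interpreters for languages other than Spanish. Nothing removes a patient seen in both periods or assigns that patient to one of them.
- **Analytic plan, repeat visits.** "If a patient is seen more than once in a given time period", only the first visit in that period is kept. The rule does not act across periods.
- **Analytic plan, estimation.** "We will estimate the proportion who screen positive for each time period and report along with 95% confidence intervals".
- **Analytic plan, comparison.** "A chi-square test will be used to provide an unadjusted comparison between the" pre and post proportions. Logistic models then compare the "proportions while controlling for clinic and patient demographic variables". Secondary outcomes use the same methods.
- **Analytic plan, sensitivity analysis.** Using all visits, "we will compare the proportion of patients who meet our primary outcome definition at any visit during the" two periods. This again gives one result per patient per period.
- **COVID-19 adjustment.** For clinics 5 and 6 the plan shortens the post "time period for these two clinics to 30 days".
- **Experimental Methods.** "The limited use dataset will contain the following data elements for each completed patient visit". The list and the safeguards below it name coded identifiers for clinic and nursing staff, but none for the patient.

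**The concern.** The chi-square test and ordinary logistic regression compute variance as if every row came from a different person. A patient with a row in each period breaks that assumption, and adjusting for clinic and demographics does not remove correlation within a person.

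Overlap is to be expected. These are primary care clinics, return visits are among the visit types, and screening is required at every provider visit. Two analysed visits by the same patient can be as little as 15 days apart (Day -1 to Day 14) and at most 133 days apart (Day -60 to Day 73). One secondary outcome is a fall in the last 6 months. Because the gap is always shorter than 6 months, the two look-back windows always overlap, and a single fall can make both rows positive.

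The appendix asks whether mPATH changes detection of depression, fall risk and safety concerns. If the test is less sensitive than the data allow, a null result is harder to interpret. The unlisted patient identifier matters for a related reason: both the first-visit rule and the any-visit analysis need visits linked within patient, as does any correction for overlap.

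**Working it through.** Appendix D states no sample size, power, alpha or expected rate, so there is no planned figure to reproduce. The check is the variance of a difference between two partly overlapping samples.

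**Inputs from the documents**
- Six clinics, with 60 days before launch and 60 days after.
- Post period cut to 30 days in clinics 5 and 6. Pre: 6 × 60 = 360 clinic-days. Post: 4 × 60 + 2 × 30 = 300 clinic-days.

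**Assumptions**
- f, the share of post-period patients also seen pre: 10% to 40%.
- ρ, the within-patient correlation of the outcome across periods: 0.3 to 0.7.
- Two-sided alpha of 5%, inferred from the 95% intervals.
- Patient numbers proportional to clinic-days, with equal daily volume.

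**Formulas.** Let n1 and n2 be the patients per period, m the number in both, and p the common proportion under the null, with q = 1 − p.

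- True variance of the difference: pq(1/n1 + 1/n2) − 2mρpq/(n1·n2). The planned analysis omits the second term.
- R = true variance / planned variance = 1 − 2mρ/(n1 + n2).
- Equal period sizes, m = f·n: R = 1 − fρ.
- Truncated plan, m = f·n2: R = 1 − fρ × 600/660 = 1 − 0.909fρ.
- Excess in the planned standard error: 1/√R − 1.
- Actual alpha: 2[1 − Φ(1.96/√R)].
- Power of the planned test where the correct standard error would give 80%: 1 − Φ(1.96/√R − 2.80).

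**Example.** Truncated plan, f = 0.3, ρ = 0.5: R = 1 − 0.909 × 0.15 = 0.864 and √R = 0.929. The standard error is 1/0.929 − 1 = 7.6% too large. The effective critical value is 1.96/0.929 = 2.11, so alpha is 3.5% and power is 76%.

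| Period sizes | f | ρ | R | SE too large by | Actual alpha | Power (80% if correct) |
|---|---|---|---|---|---|---|
| Equal | 0.1 | 0.3 | 0.970 | 1.5% | 4.7% | 79% |
| Equal | 0.3 | 0.5 | 0.850 | 8.5% | 3.4% | 75% |
| Equal | 0.4 | 0.7 | 0.720 | 17.9% | 2.1% | 69% |
| Truncated | 0.1 | 0.3 | 0.973 | 1.4% | 4.7% | 79% |
| Truncated | 0.3 | 0.5 | 0.864 | 7.6% | 3.5% | 76% |
| Truncated | 0.4 | 0.7 | 0.745 | 15.8% | 2.3% | 70% |

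At f = 0 there is no error.

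**Simulation under the null.** 10,000 replicates per case; six clinics; 300 pre-period patients per clinic; 300 post-period patients in four clinics and 150 in two; 15% prevalence; model with period, clinic, age and sex. Patient numbers and prevalence are assumed.

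| f, ρ | Chi-square alpha | Adjusted logistic alpha | Patient-clustered robust alpha |
|---|---|---|---|
| 0.1, 0.3 | 4.9% | 4.8% | 5.1% |
| 0.3, 0.5 | 3.7% | 3.4% | 4.9% |
| 0.4, 0.7 | 2.4% | 2.2% | 4.8% |

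The simulation agrees with the closed form, shows that covariate adjustment does not cure the problem, and shows that a patient-clustered variance restores the nominal level when patient overlap is the only dependence.

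**What is not affected.** Each patient appears once per period, so cross-period overlap leaves the 95% interval for each period's proportion as it is.

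**The case against.** The strongest reply is that the error is cautious and its size unknown. Point estimates are right and false positives are not inflated. At the low end the change, from 80% to 79% power, is immaterial. If the six clinics supply so many patients that power is near 100%, little is lost. This stands as a limit on the size of the effect. It does not make the standard error correct.

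The second reply is that correcting for patient overlap alone could worsen calibration if outcomes also cluster by nurse. Suppose a nurse-by-period intraclass correlation of 0.01 with 50 patients per nurse-period. The design effect is 1 + 49 × 0.01 = 1.49. In the middle truncated case the variance ratio becomes 1.49 − 0.136 = 1.354 and planned alpha about 9.2%. After a patient-only correction the ratio is 1.354/0.864 = 1.567 and alpha about 11.7%. The arithmetic is sound, but the correlation and cluster size are invented for illustration. It shows that staff clustering needs its own answer. It is no reason to rely on one error to offset another.

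Smaller points stand in part:
- The logistic variance estimator is unstated, so ordinary logistic regression is the natural reading and not an explicit statement. The any-visit analysis names no test of its own.
- Patient linkage is implied by the first-visit rule and could be done at extraction, or described in Section 8.0, which is not among the pages available here. The list as written still lacks the field.
- Unique patients need not scale with clinic-days, because 30 days may yield more than half the unique patients of 60. The truncated figures are therefore approximate, but they lie close to the equal-size ones.

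**Conclusion.** The concern holds and should be fixed. As written, patients seen in both periods supply correlated rows to methods that assume independence. The standard error and p-value of the pre/post comparison, and any interval for a difference or odds ratio, are miscalibrated wherever there is overlap and within-patient correlation. This covers the primary outcome, the secondary outcomes and, if it follows the same methods, the any-visit sensitivity analysis.

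The existence of the problem follows from the text. Its size does not: it depends on the assumed f and ρ, and ranges from negligible to a loss of about ten percentage points of power against an 80% benchmark. For this error alone the direction is conservative when the correlation is positive. No net direction is claimed once clinic or nurse clustering is considered.

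The absence of a patient identifier from the data elements does not fit the plan's own first-visit and any-visit rules, whatever f and ρ are.

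**What to change.** 1. Add a coded patient study identifier to the data elements, linking visits within and across periods, in the same style as the clinic and nurse codes.
2. Report how many patients were seen in both periods.
3. Replace the chi-square and ordinary logistic comparisons with a logistic GEE clustered on patient, with working-independence correlation and robust standard errors. Fit it first with period alone, then with clinic and demographics. Use it for the primary outcome, all secondary outcomes and the any-visit sensitivity analysis.
4. Keep the per-period proportions and their 95% intervals as written.

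Working independence leaves the planned point estimates and comparison unchanged; only the standard errors and p-values move. If overlap turns out to be small, the results will barely change. How clustering by clinic or nurse is handled should be settled separately.

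The cost is one more coded field in the extract, one extra reported count and a change of model wording. No additional patients or visits are needed.

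### Appendix D collects visit type but leaves it out of the adjusted pre/post models; the estimate could be biased if visit mix shifts between windows and visit type also predicts a positive screen (minor)

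*Combined protocol and SAP*

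**What the plan says.** Under Experimental Methods, Appendix D states: "The limited use dataset will contain the following data elements for each completed patient visit". One listed element is "Type of visit completed (for example, new patient visit, return patient visit, annual exam".

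The Analytic plan gives a chi-square test as the unadjusted comparison. It then specifies logistic regression comparing the pre and post "proportions while controlling for clinic and patient demographic variables". The demographic variables are not itemised, but visit type describes the encounter rather than the patient, so it is not naturally one of them. The same approach carries over to the other endpoints: "We will use the same analytic methods for our secondary outcomes".

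A patient seen more than once in a window contributes one record, because only the "first visit in that time period will be included in the analyses". Each analysed record therefore has a single visit type.

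The planned sensitivity analyses count a positive screen at any visit, restrict to the first four clinics, or limit post-launch data to 30 days. None of them uses visit type.

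**The concern.** In an uncontrolled before/after comparison, covariate adjustment is the main protection against a change in case mix. A clinic term removes stable differences between clinics, but not a change in mix within a clinic from one window to the next.

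Such a change is possible here. The windows (Days -60 to -1 and Days 14 to 73) fall in different calendar time, the first visit of any type is analysed, and clinics #5 and #6 have 60 days before launch against 30 after. If patients attending for one type of visit screen positive more often than the rest, a shift in mix would look like an mPATH effect or would mask one. The plan has no table by period that would reveal such a shift and no model that would remove it.

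**Working it through.** There is no figure in the plan to reproduce: Appendix D states no sample size, positivity, visit-type mix or target effect. What follows is an illustration on assumed inputs.

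**From the documents.** Model terms are period, clinic and demographics. There is one record per patient per window, and visit type is available on each record.

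**Assumed.** mPATH has no true effect. There are two visit types. Overall positivity before launch is p0 = 20%. Positivity differs between the types by d = 4 or 10 points. One type makes up 40% of pre-launch visits (25% and 55% in two equal-sized demographic groups). Its share rises after launch by s = 0, 2, 5 or 10 points.

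**Simple arithmetic, none of the shift absorbed.** Apparent post positivity is p1 = p0 + s × d, and the apparent OR is [p1/(1 − p1)] / [p0/(1 − p0)], where p0/(1 − p0) = 0.20/0.80 = 0.25.

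- s = 5, d = 4: p1 = 0.20 + 0.05 × 0.04 = 0.202; OR = (0.202/0.798)/0.25 = 1.013
- s = 5, d = 10: p1 = 0.205; OR = (0.205/0.795)/0.25 = 1.031
- s = 10, d = 4: p1 = 0.204; OR = (0.204/0.796)/0.25 = 1.025
- s = 10, d = 10: p1 = 0.210; OR = (0.210/0.790)/0.25 = 1.063

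**Logistic fit to expected counts** in one clinic stratum, with period and the demographic in the model and visit type omitted (range over d = 4 to 10 points):

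| Shift in share | None absorbed by demographics | Half absorbed | All absorbed |
|---|---|---|---|
| 0 points | 1.000 | 1.000 | 1.000 |
| 2 points | 1.005-1.013 | 1.002-1.006 | 1.000 |
| 5 points | 1.013-1.031 | 1.006-1.016 | 1.000 |
| 10 points | 1.025-1.063 | 1.012-1.031 | 1.000 |

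**Checks on the two conditions.** With d = 0 (visit type unrelated to positivity) the OR is 1.000 for every shift. With s = 0 it is 1.000 for every d. With visit type added to the model it is 1.000 in every cell.

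**Direction.** If the share falls instead of rising, the bias reverses. For s = −10 and d = 10, p1 = 0.190 and OR = (0.190/0.810)/0.25 = 0.938.

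**Sensitivity to base rate.** For the 10-point unabsorbed shift, the range is 1.045-1.113 at 10% positive and 1.019-1.048 at 30% positive.

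**The case against.** The strongest objection is that nothing in the documents shows a shift in visit mix, or that visit type predicts a positive screen. The comparison is within clinic, the windows are close together, and a patient seen in both windows contributes a first visit to each, which limits drift. Policy requires all three screens at each provider visit, so visit type should not determine whether screening is due. The four-clinic and 30-day analyses already probe the truncated windows. Clinic plus demographics is a coherent adjustment set, and adding visit type does not supply the missing concurrent control.

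Most of this stands, and it rules out the stronger reading that a reader might infer, namely that the planned estimate is biased or would be biased by any change in visit mix. A shift alone is not enough; the d = 0 check shows that. What remains is narrower. A universal screening policy equalises who should be screened, not who screens positive. The planned sensitivity analyses do not adjust for visit type. The documents do not suggest that mPATH changes visit type, so there is no evident reason to keep it out of the model.

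A reader might also infer that the other unused baseline field, "Whether patient has a diagnosis of depression in the problem list in the EHR (Y/N", belongs in the models, together with "Whether patient has an antidepressant medication listed in the active medication list (Y/N". The documents do not support that. Neither field is dated in the plan, and mPATH screening could itself change what is recorded. Medication status is also part of one secondary outcome: "Have a PHQ9 score >14 and are not currently taking a medication for depression". Leaving both out of the adjusted models is defensible.

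**Conclusion.** The point holds as a minor one. Visit type is collected for every completed visit and used nowhere in the analysis, so the plan passes over an almost free guard against a change in case mix within clinics. The adjusted OR could be biased in either direction, but only if the first-visit mix shifts and visit type predicts positivity, both after allowing for clinic and demographics.

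On the assumed inputs the distortion is none to small: at 20% positive with nothing absorbed, at most about 3% on the OR for a 5-point shift and about 6% for a 10-point shift. It reaches about 11% only in the corner case of 10% positive, a 10-point shift and a 10-point difference in positivity. With no sample size in the appendix, no false-positive rate can be attached to these figures.

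**What to change.** 1. Add the type of the patient's first visit in the period to the logistic model for the primary outcome.
2. Add it to the secondary-outcome models where event counts allow. The plan gives visit-type levels only as examples, so collapse sparse levels for outcomes likely to be rare, such as PHQ9 >19 or thoughts of self-harm.
3. Tabulate first-visit type by period, so that readers can see whether the mix moved.
4. If the data have already been analysed, keep the planned model and report the visit-type-adjusted model beside it, labelled as a post hoc sensitivity analysis.

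The cost is slightly more analysis work and a few extra model terms; no new data field is needed. mPATH use stopped in March 2020 and this version is dated 7/29/2021, so both windows had closed. The documents do not say whether analysis had begun; if it had, item 4 applies and the added model is post hoc.
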